1 ABBREVIATIONS

Abbreviation	Definition
AE	Adverse Event
ANCOVA	Analysis of Covariance
ANOVA	Analysis of Variance
BCVA	Best-Corrected Visual Acuity
BMI	Body Mass Index
CI	Confidence Interval
CMH	Cochran-Mantel-Haenszel
CRF	Case Report Forms
CSR	Clinical Study Report
DBP	Diastolic Blood Pressure
FDA	Food and Drug Administration
IOP	Intraocular Pressure
ITT	Intent-To-Treat Population
LOCF	Last Observation Carried Forward
MedDRA	Medical Dictionary for Regulatory Activities
MGD	Meibomian Gland Dysfunction
MGS	Meibum Gland Secretion Score
MGYLS	Meibomian Glands Yielding Liquid Secretion
MICD	Most Important Clinical Difference
MITT	Modified Intent-To-Treat Population
MITT2	Modified Intent-To-Treat 2 Population
OSDI	Ocular Surface Disease Index
PT	Preferred Term
SAE	Serious Adverse Event
SAP	Statistical Analysis Plan
SBP	Systolic Blood Pressure
SD	Standard Deviation
SOC	System Organ Class
SOP	Standard Operating Procedure
SPEED	Standard Patient Evaluation of Eye
TBUT	Tear Break-Up Time
TEAE	Treatment Emergent Adverse Event
VAS	Visual Analogue Scale

	TEMPLATE		
	DOCUMENT #:		TMP-191
	REVISION:		2.0
STATISTICAL ANALYSIS PLAN TEMPLATE	CC #:	836	PAGE 8 OF 25

2 SUMMARY

TITLE	A Multicenter, Vehicle-controlled, Randomized Study to Evaluate the Safety, Tolerability and Pharmacodynamics of AZR-MD-001 in Patients with Meibomian Gland Dysfunction (MGD)
PREFACE	
This Statistical Analysis Plan (SAP) describes the planned analysis and reporting for Azura protocol AZ202001 (Multicenter, Vehicle-controlled, Randomized Study to Evaluate the Safety, Tolerability and Pharmacodynamics of AZR-MD-001 (Selenium disulfide Agonist) in Patients with Meibomian Gland Dysfunction (MGD). This study is being completed to assess the safety, tolerability, and pharmacodynamics of AZR-MD-001 in patients with meibomian gland dysfunction (MGD).
 
The following documents were reviewed in preparation of this SAP:
 
 • Clinical Research Protocol AZ202001 issued 12MAR2020 • Case report forms (CRFs) issued 25JUN2020 for AZ202001
PURPOSE	The purpose of this SAP is to outline the planned analyses in support of the Clinical Study Report (CSR) for protocol AZ202001. Exploratory analyses not necessarily identified in this SAP may be performed to support the clinical development program. Any post-hoc, or unplanned, analyses not identified in this SAP will be clearly identified in the respective CSR.
STUDY OBJECTIVES	To evaluate the safety, tolerability, and pharmacodynamics of AZR-MD-001 ointment/semi-solid drug applied to the lower lid twice weekly for up to 3 months compared to its vehicle in patients with meibomian gland dysfunction (MGD).
STUDY DESIGN	Multicenter, investigator-masked, vehicle-controlled, randomized, parallel group study comparing AZR-MD-001 (0.5%) ointment/semi-solid drug and AZR-MD-001 vehicle dosed twice-weekly in the evening.
ENDPOINTS	
The study's primary efficacy sign for MGD is change from baseline to month 3 in meibum gland secretion score (MGS) (0 to 45 scale). The study's primary efficacy symptom for MGD is change from baseline to month 3 in total OSDI.
 
Other Efficacy Measures:
 
 • Change from Baseline to day 14, month 1 and month 1.5 in MGS (0 to 45 scale) • MGS score (0 to 45 scale) at each visit • Proportion of patients with an MGS score > 12 at each visit • Change from Baseline to day 14, month 1, month 1.5 and month 3 in the number of Meibomian Glands Yielding Liquid Secretion (MGYLS)

	TEMPLATE		
	DOCUMENT #:		TMP-191
	REVISION:		2.0
STATISTICAL ANALYSIS PLAN TEMPLATE	CC #:	836	PAGE 9 OF 25

	
(0 to 15 scale)
 
 • MGYLS (0 to 15 scale) at each visit • Change from Baseline to day 14, month 1, month 1.5, and month 3 in TBUT • TBUT at each visit • Proportion of patients with a TBUT score > 5 at each visit • Change from Baseline to day 14, month 1, month 1.5 and month 3 in Standard Patient Evaluation of Eye Dryness (SPEED) • SPEED at each visit • Proportion of patients with a SPEED < 6 at each visit • Change from Baseline to day 14, month 1, month 1.5 and month 3 in average visual analogue scale (VAS) • Average VAS at each visit • Change from Baseline to day 14, month 1, month 1.5 and month 3 in worst VAS • Worst VAS at each visit • Change from Baseline to day 14, month 1 and month 1.5 in Total OSDI • Total OSDI, OSDI sub-scales, and individual items from the OSDI across visits • Proportion of patients with a Total OSDI change from baseline > 4.5, the known minimally important clinical difference (MICD) for early to moderate disease, at month 3 • Proportion of patients with a Total OSDI < 13 at each visit • Number of expressible glands yielding clear meibum at day 14, month 1, month 1.5, and month 3 • Eyelid margin erythema/telangiectasias at day 14, month 1, month 1.5, and month 3 • Corneal and conjunctival staining (0 to 5 scale) at each visit 
Safety Endpoints:
 
 • Adverse events • Vital signs • Study medication tolerability as measured by the Ocular Comfort Questionnaire • Urine pregnancy test • Best-corrected visual acuity (BCVA; Logarithmic visual acuity chart) • Biomicroscopy
--	---

	TEMPLATE		
	DOCUMENT #:		TMP-191
	REVISION:		2.0
STATISTICAL ANALYSIS PLAN TEMPLATE	CC #:	836	PAGE 10 OF 25

	
 • Ophthalmoscopy • Intraocular pressure (IOP)
INTERIM ANALYSES	No interim analyses are planned for this study.
FINAL ANALYSES	All final planned analyses identified in this SAP will be completed after the last participant has completed 3-months follow up.

3 STUDY OBJECTIVES AND ENDPOINTS

3.1 STUDY OBJECTIVE

To evaluate the safety, tolerability, and pharmacodynamics of AZR-MD-001 ointment/semi-solid drug applied to the lower lid twice-weekly for up to 3 months compared to its vehicle in patients with meibomian gland dysfunction (MGD).

3.2 STUDY ENDPOINTS

3.2.1 PRIMARY EFFICACY ENDPOINTS

The study's **primary efficacy sign for MGD** is change from baseline to month 3 in meibum gland secretion score (MGS) (0 to 45 scale).

The study's **primary efficacy symptom for MGD** is change from baseline to month 3 in total OSDI.

3.2.2 OTHER EFFICACY ENDPOINTS

- Change from Baseline to day 14, month 1 and month 1.5 in MGS (0 to 45 scale)
- MGS score (0 to 45 scale) at each visit
- Proportion of patients with an MGS score > 12 at each visit
- Change from Baseline to day 14, month 1, month 1.5 and month 3 in the number of Meibomian Glands Yielding Liquid Secretion (MGYLS) (0 to 15 scale)
- MGYLS (0 to 15 scale) at each visit
- Change from Baseline to day 14, month 1, month 1.5, and month 3 in TBUT
- TBUT at each visit
- Proportion of patients with a TBUT score > 5 at each visit
- Change from Baseline to day 14, month 1, month 1.5 and month 3 in Standard Patient Evaluation of Eye Dryness (SPEED)
- SPEED at each visit
- Proportion of patients with a SPEED < 6 at each visit
- Change from Baseline to day 14, month 1, month 1.5 and month 3 in average visual analogue scale (VAS)

	TEMPLATE		
	DOCUMENT #:		TMP-191
	REVISION:		2.0
STATISTICAL ANALYSIS PLAN TEMPLATE	CC #:	836	PAGE 11 OF 25

- Average VAS at each visit
- Change from Baseline to day 14, month 1, month 1.5 and month 3 in worst VAS
- Worst VAS at each visit
- Change from Baseline to day 14, month 1 and month 1.5 in Total OSDI
- Total OSDI, OSDI sub-scales, and individual items from the OSDI across visits
- Proportion of patients with a Total OSDI change from baseline > 4.5, the known minimally important clinical difference (MICD) for early to moderate disease, at month 3
- Proportion of patients with a Total OSDI < 13 at each visit
- Number of expressible glands yielding clear meibum at day 14, month 1, month 1.5, and month 3
- Eyelid margin erythema/telangiectasias at day 14, month 1, month 1.5, and month 3
- Corneal and conjunctival staining (0 to 5 scale) at each visit

3.2.3 SAFETY ENDPOINTS

- Adverse events
- Vital signs
- Study medication tolerability as measured by the Ocular Comfort Questionnaire
- Urine pregnancy test
- Best-corrected visual acuity (BCVA; Logarithmic visual acuity chart)
- Biomicroscopy
- Ophthalmoscopy
- Intraocular pressure (IOP)

4 SAMPLE SIZE

Estimates for sample size calculations are from the first interim analysis from Azura Clinical Protocol AZ201801. The standard deviation for MGS was 3.35 units for an ineffective dose and 9.48 units for the high dose. A sample size of 12 subjects per group will have 90% power to detect a difference of 10.4 units between the active treatment group and the vehicle group using a two-sample t-test at a significance level of 0.05. The standard deviation for Total OSDI was 13.01 units for an ineffective dose and 6.79 units for the high dose. A sample size of 11 subjects per group will have 90% power to detect a difference of 15.9 units between the active treatment group and the vehicle group using a two-sample t-test at a significance level of 0.05.

The total number of randomized patients for the study will be up to approximately 30. Approximately 15 patients should have a baseline MGS score of < 6 and approximately 15 patients should have a baseline

	TEMPLATE		
	DOCUMENT #:		TMP-191
	REVISION:		2.0
STATISTICAL ANALYSIS PLAN TEMPLATE	CC #:	836	PAGE 12 OF 25

MGS score ≥ 6 and ≤ 12 . Based upon data from ongoing study AZ201801 and the simplified inclusion/exclusion criteria for this study a screen failure rate of $\sim 40\%$ is expected. Thus, ~ 42 patients will need to be screened to achieve ~ 30 patients randomized to treatment.

5 SEQUENCE OF PLANNED ANALYSES

5.1 INTERIM ANALYSES

There are no planned Interim Analyses for this study.

5.2 FINAL ANALYSES AND REPORTING

All final planned analyses identified in this SAP will be completed after the last participant has completed month 3 follow up. Any post-hoc, exploratory analyses completed to support planned study analyses, which were not identified in this SAP, will be documented and reported as necessary. Any results from these unplanned analyses will also be clearly identified in the final study report.

6 ANALYSIS POPULATIONS

6.1 INTENT TO TREAT POPULATION (ITT)

The intent-to-treat (ITT) population for this study includes all enrolled and randomized patients.

6.2 MODIFIED INTENT TO TREAT POPULATION (MITT)

The modified intent-to-treat (ITT) population for this study includes all patients randomized and, who have values at randomization, and at least 1 post-randomization value for MGS at a regularly scheduled visit (i.e., Day 14 or Month 1). All patients in the mITT population will be analyzed by the treatment received. This population will be used for the primary and secondary efficacy analyses.

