6.3 MODIFIED INTENT TO TREAT 2 POPULATION (MITT2)

The modified intent-to-treat 2 (mITT2) population will be comprised of patients who are included in the mITT and have the randomization MGS score in the study eye ≥ 6 and ≤ 12 . The mITT2 population will be analyzed by the treatment received. The primary efficacy endpoints related to MGD will be repeated using this mITT2 population as sensitivity analyses.

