6.4 SAFETY POPULATION

	TEMPLATE		
	DOCUMENT #:		TMP-191
	REVISION:		2.0
STATISTICAL ANALYSIS PLAN TEMPLATE	CC #:	836	PAGE 13 OF 25

The safety population includes all treated patients. This is the primary analysis population for safety variables; subjects are analyzed under the treatment received.

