7.2 DISPOSITION OF SUBJECTS AND WITHDRAWALS

The number and percent of subjects in each analysis population will be presented, with percentages based on the ITT Population. All subjects who provide written informed consent will be accounted for. A summary of the reasons for screen failure among subjects who signed an Informed Consent will be provided.

The frequency and percent of enrolled subjects who completed each scheduled assessment will be presented for the ITT, mITT and mITT2 populations. The number and percentage of patients exposed (i.e. initiated procedure), prematurely terminated (overall and by reason of premature termination) and completed patients will be summarized.

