7.4 PROTOCOL DEVIATIONS

Protocol deviations will be summarized in the CSR for the ITT population. This summary will include the number and percent of participants (overall and by site) with each deviation type. A listing of protocol deviations will be presented and will include deviation number, date deviation occurred, visit, type of deviation, description of deviation, and action taken.

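### mITT and mITT2 efficacy is analysed by treatment received with no as-randomised analysis, and the mITT entry rule, read literally, omits patients measured only at Month 1.5 or Month 3

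*SAP*

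**What the plan says.** The mITT set carries the primary and secondary efficacy analyses. The protocol synopsis, Protocol 9.2 and SAP 6.2 all give the same grouping rule: "All patients in the mITT population will be analyzed by the treatment received". For the subset with a study-eye MGS score of 6 to 12 at randomisation, SAP 6.3 says "The mITT2 population will be analyzed by the treatment received" and that the primary endpoints "will be repeated using this mITT2 population as sensitivity analyses". The safety set in SAP 6.4 has the same rule: "subjects are analyzed under the treatment received".

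SAP 6.1 defines an ITT set: this "population for this study includes all enrolled and randomized patients". It has no grouping rule and no efficacy use.

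To enter mITT, a patient needs values at randomisation and "at least 1 post-randomization value for MGS at a regularly scheduled visit (i.e., Day 14 or Month 1"). The synopsis and Protocol 9.2 name the same two visits.

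**The concern.** Randomisation makes the two arms comparable as assigned. Regrouping by what was dispensed gives that up whenever assignment and treatment differ, so treatment received suits a safety set better than a primary efficacy set named intent-to-treat. Protocol 6.3 has sites obtain kit numbers from the IWRS again at every later visit, so there are several occasions for a dispensing error. A patient given kits from both arms would have to be placed in an arm by a decision the plan does not define.

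The entry rule is a separate issue with a similar consequence: a patient whose Month 3 MGS was measured could be left out of the Month 3 MGS analysis.

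In either case the SAP has no as-randomised result to set beside the primary one. MGS also gates the OSDI test (SAP 7.5), so a shift near the significance threshold would affect both primary endpoints.

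**Working it through.** **Which set is used for what**

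| Set | Grouped by | Used for |
|---|---|---|
| ITT (SAP 6.1) | not stated | disposition (SAP 7.2: "with percentages based on the ITT Population"), deviations (SAP 7.4: "Protocol deviations will be summarized in the CSR for the ITT population"), demographics (SAP 8.1) |
| mITT (SAP 6.2) | treatment received | both primary endpoints (SAP 9.1, 9.2), other efficacy (SAP 9.3) |
| mITT2 (SAP 6.3) | treatment received | both primary endpoints again |
| Safety (SAP 6.4) | treatment received | safety |

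The multiple-imputation analysis in SAP 7.3 names no population and no grouping rule. The subgroup analyses in SAP 12.1 name no other set. SAP 13, the list of changes from the protocol, does not mention populations. So no efficacy analysis by randomised arm is specified, and mITT2 cannot test the grouping rule because it shares it.

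**Entry rule against the schedule**

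Protocol 1.2 lists four visits after randomisation: Day 14, Month 1, Month 1.5 and Month 3. Table 1 of the protocol schedules meibomian gland evaluation at all four. LOCF in SAP 7.3 accepts values from Day 14 onward. The entry rule names only the first two visits, so it is narrower than both the schedule and the imputation rule.

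**The plan's own figure**

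Inputs from SAP 4: SDs of 3.35 and 9.48 for MGS with a difference of 10.4; SDs of 13.01 and 6.79 for OSDI with a difference of 15.9; two-sided alpha 0.05; 90% power. The method is an unequal-variance t-test with Satterthwaite degrees of freedom.

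- MGS: SE at 12 per group = sqrt((3.35² + 9.48²)/12) = 2.90; power 0.914 (0.884 at 11).
- OSDI: SE at 11 per group = sqrt((13.01² + 6.79²)/11) = 4.42; power 0.919 (0.888 at 10).

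The stated 12 and 11 per group are reproduced.

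**Size of the entry-rule effect**

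Assumptions: about 30 patients at 1:1, so 15 per arm, with SD 3.35 for vehicle and 9.48 for active. The documents give these SDs for an ineffective dose and the high dose of the earlier study, so assigning them to these arms is an assumption.

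- One patient's share of an arm: 1/15 = 6.7%. In mITT2 (about 15 patients, 7 or 8 per arm): 1/8 = 12.5% to 1/7 = 14.3%.
- SE of the difference = sqrt((3.35² + 9.48²)/15) = 2.596.
- Omitting one patient at distance d from the mean of the other 14 shifts the arm mean by d/15.

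| d (MGS units) | Shift d/15 | Shift / 2.596 |
|---|---|---|
| 3.35 (one SD, vehicle) | 0.22 | 0.09 |
| 9.48 (one SD, active) | 0.63 | 0.24 |
| 5 (assumed) | 0.33 | 0.13 |
| 10.4 (assumed) | 0.69 | 0.27 |

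The range 5 to 10.4 is 0.5 to 1.1 SDs in the active arm but 1.5 to 3.1 SDs in the vehicle arm, so it is extreme for vehicle. Power is hardly affected: losing one patient per arm takes it from 0.965 to 0.953 for the 10.4-unit difference.

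**Size of the grouping effect**

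Assume the product received gives its full 10.4-unit effect and kit errors are unrelated to prognosis. The expected as-treated difference then stays at 10.4. The expected as-randomised difference is:

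- one vehicle patient on active: 10.4 × (1 − 1/15) = 9.71, a gap of 0.69 units or 0.27 SE;
- one swapped patient in each arm: 10.4 × (1 − 2/15) = 9.01;
- two in each arm: 10.4 × (1 − 4/15) = 7.63.

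With no kit errors the two analyses are identical.

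**The case against.** The harm is contingent, and the protocol has safeguards. The IWRS ties each kit number to the randomisation number, designated accountability staff handle products that differ in colour, and tubes are collected at every visit from Day 14 (Protocol 6.1.1, 6.2.1 and 6.3). If kit errors do occur but are unrelated to prognosis, an as-treated comparison is not systematically biased. The parenthesis in the entry rule may be loose wording, and few patients would meet it: they must lack MGS at both Day 14 and Month 1 and then return. A patient who misses two consecutive visits and cannot be reached is already lost to follow-up (Protocol 7.3), and early withdrawals have the exit assessments at the next visit (Protocol 4.2.3). The computed shifts are at most 0.27 SE. They use an unadjusted SE although the primary analysis is ANCOVA, and an SD from the high dose of the earlier study.

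Most of this stands as a limit on size. It does not change the stated rules. The controls make a wrong kit less likely but do not say how to analyse one, and deviation listings would show such a case without analysing it as randomised. That errors are unrelated to prognosis is itself an assumption, one that grouping by randomised arm does not need. A patient who misses two visits but can be contacted is not lost to follow-up, so the entry-rule case can arise.

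Two further limits stand. Even after the fix, mITT requires one post-randomisation MGS value, so it is not a full ITT analysis. The safety set also has no rule for mixed kits, though that lies outside this efficacy point.

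**Conclusion.** The concern holds in all three parts: both efficacy sets are grouped by treatment received, no as-randomised efficacy analysis is planned, and the entry rule as written can exclude a patient whose Month 3 primary outcome was observed. It should be fixed.

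The size is conditional. Neither document gives a rate of kit errors or missed visits, so the effect may be nil, and if missed visits are unrelated to outcome the expected shift from the entry rule is zero. Under the stated assumptions, one affected patient moves the MGS result by roughly a tenth to a quarter of a standard error. The case for the change rests on protecting the randomised comparison and on setting the rule before the data are seen, more than on a large expected bias.

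**What to change.** - **Grouping.** In the protocol synopsis, SAP 6.2 and SAP 6.3, and in Protocol 9.2 (which covers mITT only), state that mITT and mITT2 patients are analysed in the arm to which they were randomised. Keep treatment received for the safety population only.
- **Entry rule.** In the synopsis, Protocol 9.2 and SAP 6.2, let an MGS value at any of Day 14, Month 1, Month 1.5 or Month 3 qualify a patient for mITT.
- **Optional.** An as-treated efficacy table may be kept as a sensitivity analysis, with a stated rule for patients given kits from both arms.

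The cost is wording in four places, with no new data or visits. A protocol amendment needs ethics committee approval (Protocol 10.1). If the protocol is left as it is, the two changes should be listed as two entries in SAP 13.

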6.3 MODIFIED INTENT TO TREAT 2 POPULATION (MITT2)

The modified intent-to-treat 2 (mITT2) population will be comprised of patients who are included in the mITT and have the randomization MGS score in the study eye ≥ 6 and ≤ 12 . The mITT2 population will be analyzed by the treatment received. The primary efficacy endpoints related to MGD will be repeated using this mITT2 population as sensitivity analyses.

6.4 SAFETY POPULATION

	TEMPLATE		
	DOCUMENT #:		TMP-191
	REVISION:		2.0
STATISTICAL ANALYSIS PLAN TEMPLATE	CC #:	836	PAGE 13 OF 25

The safety population includes all treated patients. This is the primary analysis population for safety variables; subjects are analyzed under the treatment received.

7 GENERAL ISSUES FOR STATISTICAL ANALYSIS

Descriptive statistics for continuous variables will include the sample size, mean, standard deviation (SD), median, minimum, and maximum. Percent and frequencies will be provided for categorical variables. Results will be generated by treatment group.

7.1 ANALYSIS SOFTWARE

Analysis data sets, statistical analyses and associated output generated by Avania will be generated using SAS® Software version 9.4 or later, or R version 3.3.2 or later.

7.2 DISPOSITION OF SUBJECTS AND WITHDRAWALS

The number and percent of subjects in each analysis population will be presented, with percentages based on the ITT Population. All subjects who provide written informed consent will be accounted for. A summary of the reasons for screen failure among subjects who signed an Informed Consent will be provided.

The frequency and percent of enrolled subjects who completed each scheduled assessment will be presented for the ITT, mITT and mITT2 populations. The number and percentage of patients exposed (i.e. initiated procedure), prematurely terminated (overall and by reason of premature termination) and completed patients will be summarized.

7.3 METHODS FOR WITHDRAWALS AND MISSING DATA

The method of Last Observation Carried Forward (LOCF) will be used for efficacy on the mITT population. In these analyses, non-missing values recorded at visit 3 (i.e., Day 14) or later will be used to replace missing data at visits where data are not recorded.

If more than 5% of patients are missing data for MGS score or OSDI at 3 months prior to LOCF, then multiple imputation will be used for a sensitivity analysis for these endpoints. Missing MGS score at 3 months (prior to LOCF) will be imputed using a monotone linear regression multiple imputation approach for continuous outcome data. However, assuming the missing data pattern will not be completely monotone at first, then a Markov Chain Monte Carlo (MCMC) imputation will first be carried out using MGS scores at all time points where it is collected (prior to 3 months) to make a monotone missing data pattern. There will be 50 datasets generated in this manner to create 50 datasets with a

	TEMPLATE		
	DOCUMENT #:		TMP-191
	REVISION:		2.0
STATISTICAL ANALYSIS PLAN TEMPLATE	CC #:	836	PAGE 14 OF 25

monotone missing data pattern. For each of these 50 data sets, missing MGS score at 3 months will then be imputed once from a monotone multiple imputation linear regression model with independent variables: age, gender, duration of disease, and TBUT at month 3. Also included will be baseline and post-baseline non-missing MGS scores. The ANCOVA model will then be carried out on each of the resulting 50 complete datasets, with the ANCOVA results being combined across the 50 complete datasets using standard multiple imputation theory to obtain one overall p-value assessing the treatment on reduction in MGS score after accounting for missing data.

The same analysis will be conducted for missing OSDI data at 3 months if more than 5% of subjects are missing this assessment, using baseline and post-baseline non-missing OSDI in the imputation model.

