### 1.2 SCHEMA

**Study Design:** *Structure:* Multicenter, investigator-masked, vehicle-controlled, randomized, parallel group study comparing AZR-MD-001 (0.5%) ointment/semi-solid drug and AZR-MD-001 vehicle dosed twice-weekly in the evening.

Patients with MGD will be randomly assigned in a 1:1 ratio to receive either a single concentration of AZR-MD-001 ointment/semi-solid drug (i.e., 0.5%) or AZR-MD-001 vehicle.

For all dose groups a screening visit will be followed by a baseline visit 14 days later (qualification period). At the end of the qualification period patients who still exhibit signs of MGD and who can comply with dosing instructions at the baseline visit will be enrolled into a 3-month treatment period. The study flow is shown in Figure 1.

*Duration:* The total duration of study is approximately 3.5 months (from screening to study completion).

*Study Treatment Groups:* AZR-MD-001 ointment/semi-solid drug (i.e., 0.5%).

*Active Period Control:* AZR-MD-001 Vehicle

*Baseline Visit:* “Vaseline” (AZR-MD-001 Vehicle)

*Dosage/Dose Regimen:* Upon meeting inclusion/exclusion criteria patients will be randomized to AZR-MD-001 ointment/semi-solid drug (0.5%) or AZR-MD-001 vehicle administered twice-weekly, in the evening at bed time for three months.

*Randomization/Stratification:* Patients will be randomized to receive AZR-MD-001 ointment/semi-solid drug (0.5%) or AZR-MD-001 vehicle in a 1:1 treatment allocation ratio at the baseline visit.

Patients will be stratified by duration of MGD diagnosis (i.e., < 5 years or  $\geq$  5 years) and baseline MGS score (MGS score of < 6 or MGS score  $\geq$ 6 and  $\leq$  12) for the qualified eye (i.e., the eye meeting the inclusion/exclusion criteria). If the patient has 2 qualified eyes, the stratification will be based on the eye with the lower numerical MGS score. If the eyes have the same MGS score, then the right eye will be selected as the study eye.

*Visit Schedule:* Up to 6 scheduled visits: screening, randomization, day 14, month 1, month 1.5, and month 3 (exit). For patients who discontinue the study early, the month 3 visit procedures should be completed.

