### 9.2 POPULATIONS FOR ANALYSES

The safety population will include all treated patients. For safety variables, patients in the safety population will be analyzed by the treatment actually received. The modified intent-to-treat (mITT) population will be comprised of all patients randomized and, have values at randomization, and at least 1 post-randomization value for MGS at a regularly scheduled visit (i.e., Day 14 or Month 1). All patients in the mITT population will be analyzed by the treatment received. This population will be used for the primary and the secondary efficacy analyses.

The method of Last Observation Carried Forward (LOCF) will be used for efficacy on the mITT

population. In these analyses, non-missing values recorded at visit 3 (i.e., Day 14) or later will be used to replace missing data at visits where data are not recorded.

Additional imputation methods will be used for sensitivity analysis and will be outlined in the Statistical Analysis Plan (SAP).

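### LOCF as the primary missing-data method lets a Day 14 score count as Month 3, which biases the Month 3 comparison if scores are still changing, and the planned multiple imputation is not an adequate safeguard

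*SAP*

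**What the plan says.** SAP 7.3 sets the rule for efficacy: "The method of Last Observation Carried Forward (LOCF) will be used for efficacy on the mITT population". It then says that "non-missing values recorded at visit 3 (i.e., Day 14) or later will be used to replace missing data at visits where data are not recorded". Protocol 9.2 carries the same rule ("non-missing values recorded at visit 3 (i.e., Day 14) or later will be" used as replacements) and leaves other methods to the SAP: "Additional imputation methods will be used for sensitivity analysis and will be outlined in the Statistical Analysis Plan (SAP".

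The mITT set is the primary efficacy population. SAP 6.2 requires only "at least 1 post-randomization value for MGS at a regularly scheduled visit (i.e., Day 14 or Month 1"), so a patient with nothing after Day 14 enters the primary test with that score.

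Protocol 1.2 schedules "screening, randomization, day 14, month 1, month 1.5, and month 3 (exit"). MGS and OSDI are measured at every post-baseline visit (Protocol Table 1). The ANCOVA code in SAP 9.1 and 9.2 is run separately by visit, so earlier scores reach the Month 3 analysis only as carried-forward values.

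If more than 5% of patients lack a Month 3 MGS or OSDI value, "then multiple imputation will be used for a sensitivity analysis for these endpoints" (SAP 7.3). The final imputation step uses "independent variables: age, gender, duration of disease, and TBUT at month 3", together with baseline and post-baseline scores of the endpoint. Treatment is not in the list.

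Protocol 4.2.3 asks patients who withdraw early to have the Month 3 assessments at their next visit. Neither document says whether those values are analysed as Month 3.

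**The concern.** LOCF assumes that a patient's score would not have moved between the last visit and Month 3, and it analyses the filled-in value as if it had been observed. Neither document justifies that assumption. If scores are still moving, carried-forward values fall short of the Month 3 response. With equal dropout this shrinks a growing effect. With unequal dropout it also adds a difference that comes from who left rather than from the drug.

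The MGS test decides whether Total OSDI may be tested at all (SAP 7.5), so a distorted MGS result affects both primary endpoints. The data for a better analysis are already being collected: a patient who misses Month 3 can still contribute up to three earlier visits.

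**Working it through.** **1. The plan's own figure.** SAP 4 gives MGS SDs of 3.35 and 9.48, a difference of 10.4, 12 per group, 90% power, alpha 0.05. A noncentral-t calculation with Satterthwaite degrees of freedom gives about 88% power at 11 per group and 91% at 12, so 12 is reproduced. The same method gives 11 per group for OSDI (SDs 13.01 and 6.79, difference 15.9, power about 92%). At 15 per arm (half of about 30), MGS power is 96.5%.

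**2. Formula.** Let A and V be the true Month 3 mean changes on active and vehicle, dA and dV the shares missing Month 3, and m the mean fraction of the Month 3 change reached at the carried-forward visit. Then

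LOCF difference = A × [1 − dA × (1 − m)] − V × [1 − dV × (1 − m)].

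From the documents: V = 4.5, the vehicle change in the prior study (Protocol 2.2), and A = 4.5 + 10.4 = 14.9. Assumed: dropout, trajectory, and a last visit equally likely to be Day 14, Month 1 or Month 1.5.

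- Linear growth: fractions 14/90, 30/90 and 45/90, so m = 0.330 and 1 − m = 0.670.
- Saturating growth (remaining change halves every 30 days): fractions 0.316, 0.571 and 0.739, so m = 0.542.
- Plateau by Day 14: m = 1.

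**3. LOCF estimate, true difference 10.4.**

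| Missing, active/vehicle | Linear | Saturating | Day 14 plateau |
|---|---|---|---|
| 10%/10% | 9.70 | 9.92 | 10.4 |
| 20%/20% | 9.01 | 9.45 | 10.4 |
| 30%/10% | 7.7 | 8.6 | 10.4 |
| 20%/0% | 8.40 | 9.04 | 10.4 |
| 0%/20% | 11.00 | 10.81 | 10.4 |

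Example, 30%/10% linear: 14.9 × (1 − 0.3 × 0.670) − 4.5 × (1 − 0.1 × 0.670) = 11.90 − 4.20 = 7.7.

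Under linear growth with equal dropout and SDs held fixed, power at 15 per arm falls from 96.5% to 94.1% at 10% missing and 90.5% at 20%. At 12 per arm it falls from about 91% to 87% and 82%.

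**4. A small true effect.** In the prior study the 0.5% dose changed MGS by 4.9 against 4.5 on vehicle, a difference of 0.4. Under linear growth:

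- 20%/0% missing: 4.9 × (1 − 0.2 × 0.670) − 4.5 = −0.26.
- 0%/20% missing: 4.9 − 4.5 × (1 − 0.2 × 0.670) = +1.00.

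The sign depends on which arm loses patients.

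**5. No true effect.** With a change of 4.5 in both arms and 30% active against 5% vehicle missing, the formula gives −4.5 × 0.25 × 0.670 = −0.75. Simulation (15 per arm, SD 7.1, visit correlation 0.7, 20,000 runs, unadjusted t-test) gave a bias of about −0.74 and two-sided rejection of about 5.8%. The bias is against the active arm; by symmetry, the reverse dropout pattern would favour it.

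**6. Does the planned imputation rescue the result?** With 30 patients, one missing is 1/30 = 3.3% (no imputation) and two is 2/30 = 6.7% (imputation runs). The table compares mean estimates from simulation: true difference 10.4, linear growth, 15 per arm, plan SDs, visit correlation 0.6, data missing completely at random, 4,000 runs.

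| Missing per arm | LOCF | Imputed, no treatment term | Imputed, with treatment term |
|---|---|---|---|
| 10% | 9.63 | 9.52 | 10.35 |
| 20% | 9.00 | 8.74 | 10.38 |
| 30% | 8.31 | 7.97 | 10.44 |

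The imputation here is sequential regression on prior scores only; age, gender, duration and TBUT were not modelled. Without treatment, it pulls each missing patient toward the average of both arms and does no better than LOCF. Month 3 TBUT could help only when TBUT was recorded at Month 3 but MGS or OSDI was not.

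**The case against.** A reader might infer that the plan expects MGS and OSDI to keep improving to Month 3, so that LOCF must bias the result. The documents do not support that. Prior-study results for this drug are given at Month 3 only (Protocol 2.2). The only time-course statements concern other treatments, a thermal device and a mucolytic compound, which showed improvement by 1 month (Protocol 2.2 and 4.3). They prove neither a plateau nor continued growth. If there is a plateau by Day 14, or nothing is missing, there is no bias. This objection stands, and it makes the point conditional.

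A reader might also infer that LOCF threatens a false claim of efficacy. In the no-effect case examined, rejection rises only to about 5.8% and the bias runs against the drug. With equal dropout and a growing effect the bias is toward no effect. Lost power is the likelier cost, and at 10% missing per arm it is small. This stands too, although greater loss from the vehicle arm would push the other way.

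The plan does include multiple imputation for both primary endpoints, with 50 datasets and a trigger that two missing patients would meet. It would be wrong to say it is ignored or rarely used. But it leaves LOCF as the primary result and, as listed, omits treatment.

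The protocol also tries to obtain exit assessments from early leavers. That helps only if those values are not relabelled as Month 3; if they are, a mixed model inherits the same problem.

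Finally, the simulations used sequential regression as a stand-in, not the mixed model proposed below. That is a fair limit on the evidence for the exact replacement.

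**Conclusion.** The point holds in conditional form. LOCF is the primary method, and a score from as early as Day 14 can be analysed as Month 3. Bias arises when Month 3 data are missing and scores are still changing after the carried-forward visit. Under linear growth and the planning difference of 10.4, the loss is about 0.7 units at 10% missing per arm, 1.4 at 20%, and 2.7 at 30% active and 10% vehicle. It is smaller with saturating growth and zero with a Day 14 plateau. These sizes rest on assumed dropout, trajectory and distribution of last visits, and are illustrations rather than predictions.

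The change is still worth making. Nothing in the documents supports LOCF's no-change assumption, and the planned imputation does not correct for it as written. It should be made, but the trial is not invalid without it. Confidence is medium.

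**What to change.** In SAP 7.3, 9.1 and 9.2 and Protocol 9.2 (with the ANCOVA wording in Protocol 9.4.2 brought into line):

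- **Primary analysis:** a repeated-measures mixed model on observed changes at Day 14, Month 1, Month 1.5 and Month 3, with treatment, visit, treatment-by-visit, baseline value of the endpoint and duration stratum, plus MGS stratum for OSDI. Use REML, Kenward-Roger degrees of freedom and an unstructured covariance, and name in advance a simpler covariance to use if the model does not converge. The Month 3 treatment contrast is primary.
- **Early exits:** analyse exit assessments at the visit when they actually took place, not as Month 3.
- **Sensitivity:** keep the LOCF ANCOVA. In the multiple imputation, add treatment to the model and drop Month 3 TBUT.

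The cost is wording in two documents and a few lines of code. The model relies on data being missing at random, and with about 30 patients the fallback covariance may well be needed.
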